Inclusion criteria: 
 1. Enrollment in the Longitudinal Study of the Porphyrins (7201) 2. Willing to sign informed consent form (and provide assent if participant is a minor) 3. Biochemical findings- a marked increase in erythrocyte protoporphyrin [total erythrocyte protoporphyrin >200 ug/dL, or more than 1.5-fold increase (relative to ULN of 80 ug/dL)], with a predominance of free protoporphyrin (85-100% in EPP and 50-85% in XLP). 4. Molecular findings – one of the following: 
 a. A disease causing FECH mutation trans to the IVS3-48C>T low expression FECH allele b. Two disease-causing FECH mutations c. A gain-of-function ALAS-2 C-terminal deletion/exon 11 mutation (in XLP). 
If no mutation is found and subjects fulfill criteria 1-3 they are eligible for enrollment

Exclusion Criteria: 
 1. Elevations of porphyrins in urine, plasma or erythrocytes due to other diseases (i.e. secondary porphyrinuria or porphyrinemia), such as liver and bone marrow diseases [13].

2. A diagnosis of porphyria that cannot be documented by review of existing medical records or repeat biochemical or DNA testing.

Primary Objectives:

1. Systematic characterization of the phenotypic, psychosocial, biochemical, and molecular data for EPP and XLP;
2. Longitudinal investigation and analysis of pertinent issues involved in prognosis for the erythropoietic protoporphyrias, including morbidity, development of disease complications, and outcomes of commonly used treatments, as well as more advanced treatments such as liver or bone marrow transplantation, and new photoprotective drugs now under investigation;
3. Identification of biochemical features (biomarkers) that may predict future symptomatic episodes so that interventions can be initiated before symptoms develop; and
4. Provide a resource of well-documented data, samples, and subjects that may be available for other studies, including genetic studies (predictors, biomarkers, modifying genes, etc.), mechanistic investigations, and clinical trials.

Statistical Considerations (sample size and analysis plan):

1. Sample size: 150
2. Analysis plan:
 - a. Correlations between QoL scale scores, clinical severity measures and genotype will be computed. The clinical course and severity of patient will be described.

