 - b. Relationships between clinical and laboratory values will be evaluated in longitudinal mixed effect models. We will develop models that capture the combined frequency and severity of disease manifestations while accounting for age of onset, protoporphyria subtype (EPP and XLP), and genotype. A sample size of 150 (assuming a minimum of 3 follows ups per patient, a correlation of 0.7 among outcomes over time from the same subject, a variance of outcome equal to 1 and a compound symmetric covariance structure) yields 91% power to detect a moderate interaction ($\beta=0.4$) between time and an associated factor of interest.
 - c. A severity score based on predictive demographic and clinical characteristics will be developed
 - d. After 100 participants are enrolled, the mean score of the Hospital Anxiety and Depression Scale (HADS) will be computed and compared to the general population value. A sample size of 100 yields 90% power to detect a 20% difference in HAD-scale between the general population and our sample at the .05 significance level. The illness Perception Questionnaire and EPP/XLP-specific questionnaire will also be scored.
 - e. During this interim look at $n=100$, we will re-evaluate the estimates used in our initial power calculation that yielded a sample size of 150 and determine whether the study needs to be extended beyond this point to examine correlations of QoL scale scores with clinical severity and genotypes

Sponsors (federal, state, foundation and industry support): National institutes of Health (NIH)

1. Protocol Overview

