- 1) Participants and their family members known to the investigators who can be re-contacted and consented for inclusion, or who have previously consented for the procedures that are part of this study.
- 2) Individuals referred by the American Porphyria Foundation with known or suspected porphyria.

- 3) Individuals referred by physicians and other sources.

4.A. Inclusion criteria

There will be no exclusions based on age, race, ethnicity, or gender for this study. Inclusion criteria are based on 1) clinical features, 2) biochemical findings, as documented by laboratory reports of porphyria-specific testing performed after 1980, and 3) molecular findings documenting the identification of a mutation in a porphyria-related gene. Absolute values are preferred for diagnostic biochemical thresholds. Fold increases in comparison to an upper (or lower) limit of normal (ULN or LLN) are also acceptable, but are complicated by considerable variation between laboratories in normal limits. Equivocal biochemical measurements may require confirmation by a consortium reference laboratory. Provision is made for enrolling relatives who may not have symptoms but have biochemical or molecular documentation of a porphyria.

1. Enrollment in the Longitudinal Study of the Porphyrins (7201)
2. Willing to sign informed consent form (and provide assent if participant is a minor)
3. Biochemical findings- A marked increase in erythrocyte protoporphyrin [total erythrocyte protoporphyrin >200 ug/dL, or more than 1.5-fold increase (relative to ULN of 80 ug/dL)], with a predominance of free protoporphyrin (85-100% in EPP and 50-85% in XLP).
4. Molecular findings – one of the following:
 - a. A disease causing FECH mutation trans to the IVS3-48C>T low expression FECH allele
 - b. Two disease-causing *FECH* mutations
 - c. A gain-of-function *ALAS-2* C-terminal deletion/exon 11 mutation (in XLP)

If no mutation is found and subjects fulfill criteria 1-3 they are eligible for enrollment

We expect to enroll 150 patients with EPP/XLP.

4.B. Exclusion Criteria

We will exclude cases with elevations of porphyrins in urine, plasma or erythrocytes due to other diseases (i.e. secondary porphyrinuria or porphyrinemia), such as liver and bone marrow diseases [Gibson 2000]. We will also exclude patients with a prior diagnosis of porphyria that cannot be documented by review of existing medical records or repeat biochemical or DNA testing.

4.C. Recruitment and Enrollment of Subjects

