Disease Severity Score: Clinical and laboratory values assessed above will be considered potential variables to be included in an overall disease severity score. The distributions of the proposed variables to be included in the severity score will be assessed for utility to the severity score calculation. Considerations for variable utility include sufficient variability in the disease population and interrelationships with other proposed variables (if two variables are highly correlated one will be removed from the score calculation). Variables chosen to be included in the severity score will be assigned categorical ranks based on individual severity and then summed to get an overall disease severity score. The utility of the severity score will be assessed by correlating the score with clinical outcomes.

Psychosocial Impact: The following questionnaires will be administered: a) the Hospital Anxiety and Depression Scale will be used to determine the levels of anxiety and depression in these patients. These data will be scored as per the established protocol and compared to the published age-matched norms; b) the Illness Perception Questionnaire will determine the disease impact and understand how patients think and feel about their disorder. This questionnaire will determine if certain groups, such as younger adults, are more significantly impacted by this disease. The questions are scored on a Likert scale and higher scores indicate greater impairment; c) a recently validated EPP/XLP-specific questionnaire

developed in Europe will more specifically evaluate disease impact on daily functioning. After the target enrollment of n=100 is reached, we will begin the analysis.

Our primary outcome is verifying that EPP and XLP patients have higher than normal anxiety and depression. We will compare the mean Hospital Anxiety and Depression Scale (HADS) of our sample with the general population Scale (mean = 9.82, SD=5.98) (16). The null hypothesis is that there is no difference in HADS score between the general population and EPP/XLP patients.

With a sample size of 100, using a two-tailed 0.05 level one-sample t-test we will be able to detect a 20% difference in scale between the general population and our sample with 90% power.

Secondary analyses include:

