- 1) Characterizing EPP and XLP Illness Perception via the Illness Perception Questionnaire, dermatology-specific QOL via the Dermatology Life Quality Index and EPP-specific QOL via the EPP/XLP specific questionnaire. The mean and standard deviation of each scale in our sample will be assessed.
- 2) Scores for all four QOL assessments will be analyzed; FECH and ALAS 2 mutations correlations will be sought with clinical parameters, disease severity score and genotypes.

Secondary analyses will inform whether a study extending beyond 100 patients will be needed to examine correlations of QOL scale scores with clinical severity and genotypes.

6. B Power Calculation

For the proposed analyses, the statistical powers are of two sided tests, with 0.05 level of significance.

Linear mixed effects model: We may assume, for example, that 150 participants will have at least 3 follow up visits per subject. Taking into account the correlation among outcomes over time from the same subject, the main interest is in determining whether the regression coefficient of the interaction between time and covariate of interest is zero or not. Using GPower 3.0, Table 6-1 shows the results when the variance of outcome is equal to 1, where ρ and β denote correlation among repeated outcome measures and effect size of the interaction, respectively. In this calculation, we assume compound symmetry for the covariance structure of repeated outcome measures from the same subject and the same number of subjects in each group with/without a potential factor of interest. The study is certain to detect moderate ($B \geq 0.4$) differences in the analysis.

Table 6-1. Power calculation for linear mixed effects model based on the most common types of porphyria (AIP and PCT)

Sample size	ρ	B for time x factor of interest	Power
150	0.5	0.3	0.45
		0.4	0.72
		0.6	>0.99
	0.7	0.3	0.67
		0.4	0.91
		0.6	>0.99

7. Data Management

All study data will be collected via systems created in collaboration with the RDCRN Data Management and Coordinating Center and will comply with all applicable guidelines regarding patient confidentiality and data integrity.

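### The protocol gives two unreconciled enrolment figures, 100 and 150, with no rule linking them, and the stated 91% power of the longitudinal model belongs only to 150

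*Combined protocol and SAP*

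**What the plan says.** **Places that use 150.** The synopsis states "Sample size: 150". Section 4.A says "We expect to enroll 150 patients with EPP/XLP". Section 6.B begins its power calculation with "We may assume, for example, that 150 participants will have at least 3 follow up visits per subject", and every row of Table 6-1 is for 150.

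**Places that use 100.** Section 6.A, under Psychosocial Impact, says "After the target enrollment of n=100 is reached, we will begin the analysis". It bases the one-sample HADS test on 100 patients with 90% power. After listing the secondary analyses, which include correlations of QoL scores with severity and genotype, it says "Secondary analyses will inform whether a study extending beyond 100 patients will be needed" to examine those correlations.

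**The place that mentions both.** Synopsis item 2.e describes n=100 as an interim look. The look re-examines the estimates behind the 150 and is then to "determine whether the study needs to be extended beyond this point to examine correlations of QoL scale scores with clinical severity and genotypes".

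No section gives a criterion for that decision. None says that enrolment stops at 100, and none says that it continues to 150 whatever the look shows.

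**The concern.** If 150 were settled, going beyond 100 would not be an open question. If 100 is the target, the power statements in synopsis item 2.b and section 6.B describe a study larger than the one planned. The two descriptions of the n=100 look also differ on what drives the decision: the power inputs in item 2.e, the secondary analyses in 6.A.

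This matters because the two figures come from different calculations. Having enough patients for the HADS comparison says nothing about whether there are enough for the time-by-factor interaction in the mixed model, which serves the longitudinal natural-history objective. Section 6.B treats detection of B of 0.4 or more as assured, and that claim would be harder to defend at 100. A site or analyst working from 6.A alone could reasonably take 100 as the end of enrolment.

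**Working it through.** **Inputs**
- Level: section 6.B, "the statistical powers are of two sided tests, with 0.05 level of significance".
- Mixed model: synopsis item 2.b, "a correlation of 0.7 among outcomes over time from the same subject, a variance of outcome equal to 1", with compound symmetry. Section 6.B adds equal groups and Table 6-1 a second correlation, 0.5. B = 0.4.
- HADS: section 6.A, mean 9.82, SD 5.98, 20% difference, n = 100, one-sample t-test.
- No dropout rate is given, so none is applied.

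**1. What 100 is for**

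Difference = 0.20 × 9.82 = 1.964. Standardised, d = 1.964 / 5.98 = 0.328. Noncentrality = 0.328 × √100 = 3.28. With 99 degrees of freedom the noncentral t gives power **0.902**, against 90% stated. This reproduces.

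**2. What 150 is for**

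The protocol does not say how B was converted to the effect size f that the power program uses, so two mappings were tried.

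*Mapping (a), assumed:* three occasions, with the groups differing by B at one of them. Then f = B / (3√2) = 0.2357 × B, the noncentrality is λ = f² × N × 3 / (1 − rho), and the test is F with 2 and 2(N − 2) degrees of freedom.

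For N = 150, rho = 0.7, B = 0.4: f² = 0.16 / 18 = 0.00889, λ = 0.00889 × 150 × 3 / 0.3 = 13.33, power **0.912** against 0.91 stated.

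| rho | B | Stated, N=150 | Mapping (a), N=150 |
|---|---|---|---|
| 0.5 | 0.3 | 0.45 | 0.456 |
| 0.5 | 0.4 | 0.72 | 0.713 |
| 0.5 | 0.6 | >0.99 | 0.973 |
| 0.7 | 0.3 | 0.67 | 0.683 |
| 0.7 | 0.4 | 0.91 | 0.912 |
| 0.7 | 0.6 | >0.99 | 0.999 |

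Five cells agree to within 2 percentage points. The cell at rho 0.5, B 0.6 does not reproduce, but nothing below depends on it.

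*Mapping (b), assumed:* a linear trend over four occasions (baseline and three follow-ups), B being the between-group difference in total change, normal approximation. The slope difference is B/3, its standard error is √[4(1 − rho) / (5N)], and the 5 is the sum of squared centred times. For N = 150, rho = 0.7, B = 0.4: 0.1333 / 0.0400 = 3.33, power = Φ(3.33 − 1.96) = **0.915**.

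**3. The same model at 100**

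- Mapping (a), rho 0.7: λ = 0.00889 × 100 × 3 / 0.3 = 8.89, power **0.758**. At rho 0.5: λ = 5.33, power **0.525**.
- Mapping (b), rho 0.7: 3.33 × √(100/150) = 2.72, power **0.777**. At rho 0.5: 2.58 × √(100/150) = 2.11, power **0.559**.
- No mapping, only rescaling the stated powers: for 0.91, (1.341 + 1.960) × √(100/150) = 2.695, power **0.769**. For 0.72, (0.583 + 1.960) × √(100/150) = 2.076, power **0.546**.

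At B = 0.4 the three routes give about 0.76 to 0.78 at rho 0.7 and 0.53 to 0.56 at rho 0.5.

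**4. Who contributes to the 100**

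Table 1 restricts HADS to participants aged 18 or over, and section 8.A includes children. One hundred enrolled participants therefore yield 100 HADS scores only if all are adults. The adult share is not given. As an illustration, the HADS calculation above gives 0.827 with 80 scores and 0.706 with 60.

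**The case against.** The strongest reply is that the passages can be read together: 100 triggers the HADS analysis, 150 is the cohort for the mixed model, and the 6.A sentence concerns only the number needed for the QoL correlations. It sits under Psychosocial Impact, 6.B follows directly with 150, and section 5.E says that the study has no discontinuation rules. That reading is coherent and may be what was meant. It still leaves 100 described as the target, an extension beyond 100 left open, and an unclear reference point in item 2.e.

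Three stronger readings are tempting, and the documents do not support them.

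- *That the cohort will, or by rule may, close at 100.* No section says so. It is one reading of 6.A, and the power loss is conditional on it.
- *That 150 is fixed elsewhere and 6.A overrides it.* Section 4.A words 150 as an expectation, 6.B offers it as an example, and item 2.e provides for its own re-evaluation at 100.
- *That the n=100 look inflates the false-positive rate of the QoL correlations.* Testing at 100 and, if non-significant, again at 150 would give about 0.077 instead of 0.05. But the plan states neither a significance-triggered extension nor a re-test. These are secondary correlations to be computed and described, and no error claim is made here.

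It is also fair to say that a sponsor studying a rare disease may wish to revisit its sample size. That is an argument for stating the rule.

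**Conclusion.** The concern holds as an inconsistency in the enrolment target. The protocol gives 100 and 150 without saying how they relate, describes the n=100 decision in two different ways, and supplies no rule. The figures are not interchangeable, because each reproduces the stated power of a different analysis.

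If enrolment ended at 100, the 91% stated for the longitudinal interaction would fall by about 13 to 15 percentage points at rho 0.7, and the 72% at rho 0.5 by about 16 to 19. These sizes rest on B = 0.4, variance 1, compound symmetry, equal groups, no dropout and, for two of the three routes, an assumed mapping of B. The route that only rescales the stated powers gives a similar answer. If enrolment does run to 150, no power is lost and the defect is one of wording.

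**What to change.** 1. In 6.A, stop calling 100 the enrolment target. Say that the psychosocial analysis begins once 100 adults have a HADS score, and that this triggers that analysis only. Counting scored adults, not the first 100 enrolled, preserves the n behind the 90%.
2. State in 6.A and the synopsis that enrolment continues to the stated 150 for the longitudinal model.
3. Reword the closing sentence of the secondary analyses in 6.A and synopsis item 2.e so that both describe one review at n=100. It should cover the power inputs (variance, within-subject correlation, follow-ups per patient) and bear only on extension beyond 150. Label any QoL, severity and genotype correlations reported then as descriptive.
4. If the sponsor does intend that enrolment may stop at 100, state that rule and restate the mixed-model power at 100 beside Table 6-1.

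Under items 1 to 3 the cost is wording, with no patients beyond 150. The drawbacks are that inferential results for the correlations wait until 150 are enrolled, and that the HADS analysis starts later than the 100th enrolment if children are among the first 100.

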6. Statistical Considerations

6.A Analysis Plan

General Statistical Considerations

Natural history study and genotype analyses: This is an observational study aimed to provide a systematic description of the severity and clinical course of each patient with the EPP phenotype, develop a severity score and correlate genotype with phenotype for EPP and XLP. Continuous variables representing patient demographic and clinical characteristics will be summarized using means and standard deviations or medians and quartiles as appropriate, while categorical variables will be summarized by frequencies with 95% confidence intervals.

A major objective will be to identify the FECH and ALAS2 mutations in each patient with the EPP-phenotype. In patients with the phenotype and no detectable FECH or ALAS2 mutations identified, a second independent blood sample will be obtained to confirm the absence of FECH and ALAS2 mutations, followed by whole exome sequencing. Exome analysis will be performed at the Mount Sinai Institute for Genomics and Multiscale Biology as described above in more detail.

Clinical and Laboratory Analyses: Clinical and laboratory measurements will be collected/described at each visit. We will develop models that capture the combined frequency and severity of disease manifestations while accounting for age of onset, protoporphyria subtype (EPP and XLP), protoporphyrin levels and genotype. To account for multiple observations obtained for each patient during the follow-up, we will develop linear mixed effects models that account for the main effect of interest and its change over time, correlated data associated with repeat measurements on the same persons, random effects of clinical center and patient, as well as the effects of confounding variables and any modifiers of the main effect. To assess the statistical significance of the effects of biochemical levels alone and these levels by age of patient, we will use a t-test to evaluate whether the coefficient of the interaction between biochemical level alone and biochemical levels by age differs from zero.

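### Table 6-1 is not reproduced by the single time-by-factor coefficient test that section 6.B describes, and its entry of >0.99 at ρ = 0.5, B = 0.6 should be about 0.96 to 0.98

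*Combined protocol and SAP*

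**What the plan says.** Section 6.B states that "the statistical powers are of two sided tests, with 0.05 level of significance" and supposes that "150 participants will have at least 3 follow up visits per subject". The hypothesis of interest is "determining whether the regression coefficient of the interaction between time and covariate of interest is zero or not". Section 6.A is on the same footing: for the biochemical effects, "we will use a t-test to evaluate whether the coefficient of the interaction" differs from zero.

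The calculation is described as follows: "Using GPower 3.0, Table 6-1 shows the results when the variance of outcome is equal to 1". It assumes compound symmetry and equal numbers with and without the factor. B is called the effect size of the interaction and is given no time unit. The printed powers for N = 150 are:

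| ρ | B = 0.3 | B = 0.4 | B = 0.6 |
|---|---|---|---|
| 0.5 | 0.45 | 0.72 | >0.99 |
| 0.7 | 0.67 | 0.91 | >0.99 |

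The text before the table treats detection of differences with B of 0.4 or more as certain. The table title says the figures are "based on the most common types of porphyria (AIP and PCT", although this study enrols EPP and XLP. The synopsis (analysis plan, item b) carries one cell forward: under ρ = 0.7 and β = 0.4 the design "yields 91% power to detect a moderate interaction".

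**The concern.** A power table should follow from the test and the inputs stated beside it. Here the test is a single coefficient and the inputs are nearly complete, so the table can be checked, and it does not come out. One cell also rises too fast for its own row.

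Three items needed to repeat the calculation are absent: the time unit of B, whether baseline counts as an occasion, and the GPower procedure. The unit matters because section 4.E.1 puts follow-up at every 1 to 2 years, so change per visit, per year and over all follow-up are different quantities.

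The calculation is also meant to be used again. Item e of the synopsis analysis plan says the inputs behind the sample size of 150 will be re-examined at n = 100, when an extension will be considered. That cannot be done cleanly while the effect has no unit.

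**Working it through.** **Inputs.** From section 6.B: N = 150, hence 75 per group; variance 1; compound symmetry with ρ = 0.5 or 0.7; two-sided α = 0.05; B = 0.3, 0.4, 0.6; at least 3 follow-up visits. Assumptions, because the plan is silent: equally spaced occasions, complete data, and m = 3 occasions (follow-ups only) or m = 4 (with baseline).

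**Formula.** For the difference in slope between two groups, SE = √[(1 − ρ)/S × (1/75 + 1/75)], where S is the sum of squared deviations of the time scores from their mean. Power comes from the noncentral t with noncentrality B/SE and 148(m − 1) df.

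**Time scores.** If B is total change, time runs from 0 to 1:
- m = 3: S = 0.25 + 0 + 0.25 = 0.5
- m = 4: S = 2(0.25) + 2(1/36) = 0.556

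If B is change per visit, S = 2 (m = 3) or 5 (m = 4).

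**The headline cell first (ρ = 0.7, B = 0.4, total change).**
- m = 4: SE = √(0.3/0.556 × 2/75) = 0.120; B/SE = 3.33; power 0.914. The printed 0.91 is reproduced.
- m = 3: SE = √(0.3/0.5 × 2/75) = 0.1265; B/SE = 3.16; power 0.88.

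**All six cells.**

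| Reading | ρ = 0.5: B = 0.3 / 0.4 / 0.6 | ρ = 0.7: B = 0.3 / 0.4 / 0.6 |
|---|---|---|
| Printed | 0.45 / 0.72 / >0.99 | 0.67 / 0.91 / >0.99 |
| Total change, m = 3 | 0.45 / 0.69 / 0.96 | 0.66 / 0.88 / 0.997 |
| Total change, m = 4 | 0.49 / 0.73 / 0.97 | 0.70 / 0.91 / 0.999 |
| Per visit, m = 3 | 0.956 / 0.998 / >0.999 | 0.997 / >0.999 / >0.999 |
| Per visit, m = 4 | >0.99 throughout | >0.99 throughout |

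Three occasions miss the printed 0.72 and 0.91; four miss 0.45 and 0.67. Neither gives >0.99 at ρ = 0.5, B = 0.6. The per-visit reading is far from the 0.45, 0.72 and 0.67 printed.

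**Consistency within the ρ = 0.5 row.** This needs no time scale. For a 1-df test the noncentrality is proportional to B, so each cell predicts the others (normal approximation):
- From 0.72 at B = 0.4: noncentrality 1.960 + 0.583 = 2.543. Times 0.6/0.4 gives 3.81, and power Φ(3.81 − 1.96) = 0.97.
- From 0.45 at B = 0.3: noncentrality 1.960 − 0.126 = 1.834. Times 0.6/0.3 gives 3.67, and power Φ(3.67 − 1.96) = 0.96.
- In reverse, 0.99 at B = 0.6 needs 1.960 + 2.326 = 4.286. That implies power 0.57 at B = 0.3 and 0.815 at B = 0.4, against 0.45 and 0.72 printed.

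Allowing 2 or 3 df instead, with the scale left free, every value that fits the four cells below the ceiling to within 2 points gives 0.97 to 0.98 at ρ = 0.5, B = 0.6. The conclusion on that cell therefore does not depend on which of these tests was run.

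**The certainty claim.** The table's own 0.72 at ρ = 0.5, B = 0.4 leaves a 28% chance of missing the effect; the 0.91 at ρ = 0.7 leaves 9%.

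**The case against.** The strongest reply is that the table is nearly right where it matters. The described test with four occasions and B as total change gives 0.914 for the only cell quoted in the synopsis. The other cells below the ceiling differ by at most about 4 points, and the faulty cell moves only from >0.99 to about 0.97. The section offers its assumption of three follow-ups as an example, the primary HADS comparison is powered separately, and the inputs are to be revisited at n = 100. All of this stands, and it keeps the point to a correction of the record.

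A reader might go further and infer that the table came from an omnibus group-by-occasion F-test. With B as a group difference at one occasion only, that test gives 0.456/0.713/0.973 and 0.683/0.912/0.999 for three occasions, and 0.442/0.707/0.976 and 0.676/0.914/0.999 for four. These are close, but at two decimals only one of the four cells below the ceiling agrees in either version. A 1-df test with a freely chosen scale comes within 1.6 points of those four cells, against 1.0 for the omnibus test, and unequal visit spacing could supply such a scale. The documents name the software but no procedure, so the origin of the figures cannot be established.

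A reader might also infer that the power at ρ = 0.7, B = 0.4 could lie anywhere from 0.80 to above 0.99. Those ends come from an omnibus test on a linear change and from a per-visit slope, and the table's other cells rule out both. The title naming AIP and PCT might suggest inputs borrowed from other diseases, but every stated input is generic, so it supports no more than a labelling error.

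**Conclusion.** The point holds in limited form. Table 6-1 is not the output of the 1-df test described under any equally spaced coding of 3 or 4 occasions. One cell is wrong whichever of the 1- to 3-df tests was used: ρ = 0.5, B = 0.6 should read about 0.96 to 0.98. The certainty claim for B of 0.4 or more contradicts the table's own 0.72. The 91% is sound if B means total change over four occasions, and about 3 points too high if there are three. Nothing here shows that 150 participants is too few.

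These figures rest on complete data, equal groups, variance 1, compound symmetry and equal spacing. All but the complete data and the spacing are stated in section 6.B.

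**What to change.** In section 6.B:
- State the unit of B (total change in SD over follow-up, or SD per year with the visit spacing), the number of occasions, whether baseline is one of them, and the procedure used.
- Recompute all six cells for the 1-df coefficient. With B as total change over four occasions they are 0.49, 0.73, 0.97 (ρ = 0.5) and 0.70, 0.91, 0.999 (ρ = 0.7). The ρ = 0.5, B = 0.6 cell becomes about 0.97.
- Replace the certainty sentence with the computed powers for B = 0.4: about 0.7 at ρ = 0.5 and about 0.9 at ρ = 0.7.
- Correct the table title so that it refers to EPP and XLP.

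In synopsis item b, quote the matching figure with the same definition of the effect: 91% for four occasions, or about 88% for three.

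The cost is one recalculated table and a few sentences. Enrolment, visits and data collection are unaffected.
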